9.2 Subject Accountability

A summary of subject disposition and investigational product disposition will be provided for all subjects enrolled in the study. A subject disposition listing, noting inclusion in each analysis subset, will be provided for all subjects enrolled.

A subject listing noting duration of investigational product administration, reason for discontinuation of treatment, and reason for discontinuing study will be provided. A list of subjects screened but not enrolled (screen failures) will be provided.

In addition, significant known protocol deviations will be noted for individual subjects; a summary table may also be provided.

9.3 Important Protocol Deviations

Important Protocol Deviations (IPDs) categories are defined by the study team before the first subject's initial visit and updated during the IPD reviews throughout the study prior to database lock. These definitions of IPD categories, subcategory codes, and descriptions will be used during the course of the study. Eligibility deviations are defined in the protocol.

9.4 Demographic and Baseline Characteristics

Descriptive statistics will be presented for age, height, weight.

Frequency counts and percentage will be presented for gender, ethnic group, baseline disease stage, lines of prior oncology therapeutics, and primary tumor type.

A listing of the demographic and baseline characteristics will be provided.

Lists of medical/surgical history, including prior chemotherapy, will be provided.

9.5 Efficacy Analyses

Unless otherwise specified, all subjects that are enrolled and receive at least one administration of AMG 596 at the MTD (the efficacy analysis set) will be included in the analysis of the secondary efficacy endpoints.

The following methods will be used with Kaplan-Meier analyses of efficacy endpoints.

- Estimation of the median and CI will use the Brookmeyer and Crowley (1982) method
- Landmark estimates (eg, 6 month PFS) will be estimated using the Kaplan-Meier curve and CI using Greenwood's formula to estimate the standard error (see [Kalbfleisch J.D. and Prentice R.L. \(1980\)](#))

9.5.1 Analyses of Efficacy Endpoint(s)

Duration of Response:

Descriptive statistics will be provided. As appropriate, duration of response will be analyzed using the Kaplan-Meier method. Kaplan-Meier curves and estimates will be presented. Subjects without an objective response are excluded from the analyses of this endpoint. The median duration of response and other percentiles, as appropriate, and 80% CI will be presented. The percent of subjects with durable response at 6 and 12 months along with 80% CI will be presented.

Time to Response:

Descriptive statistics will be provided. As appropriate, time to response will be analyzed using the Kaplan-Meier method. Kaplan-Meier curves and estimates will be presented. The median time to response and other percentiles, as appropriate, and 80% CI will be presented.

Time to progression:

Time to progression will be analyzed using the Kaplan-Meier method. Kaplan-Meier curves and estimates will be presented. The median time to progression and other percentiles, as appropriate, and 80% CI will be presented. The percent of subjects who are progression-free at 6 and 12 months along with 80% CI will be presented.

Objective Response Rate:

Objective Response Rate will be analyzed using RANO Evaluable Analysis Set.

The number and proportion of patients with an objective response will be tabulated by AMG 596 dose received (MTD or other doses). An exact 80% confidence interval will be calculated using Clopper-Pearson method ([Clopper and Pearson, 1934](#). See [Appendix B](#) for code fragment) for the OR rate for all subjects in part 2 and those in part 1 treated at RP2D/MTD for each group.

Progression Free Survival:

Progression free survival (PFS) will be analyzed using the Kaplan-Meier method. Kaplan-Meier progression free survival curves and estimates will be presented. The median PFS and other percentiles, as appropriate, and 80% CI will be presented. The percentage of subjects alive and progression-free at 6 and 12 months along with 80% CI will be presented.

Response Criteria:

Response criteria will be analyzed using RANO Evaluable Analysis Set.

The number and percentage of subjects in each response category (CR, PR, SD and PD) will be tabulated by AMG 596 dose received (MTD or other doses).

9.6 Safety Analyses

9.6.1 Adverse Events and Disease-related Events

The Medical Dictionary for Regulatory Activities (MedDRA) version [21.1] or later will be used to code all events categorized as adverse events, disease-related events, to a system organ class and a preferred term.

Treatment-emergent adverse events are events with an onset after the administration of the first dose of investigational product.

The subject incidence of adverse events will be summarized for all treatment-emergent adverse events, serious adverse events, disease related adverse events, adverse events leading to withdrawal of investigational product, and fatal adverse events, adverse events of interest (if applicable). The identification of adverse events of special interest is a continuous process. Events may be identified and documented as the safety profile of the drug is characterized. The severity of each adverse event will be graded using CTCAE version 4.0 criteria. Grading for Cytokine Release Syndrome (CRS) will be performed according to the recommendations provided by [Lee et al, 2014](#) (Appendix E of the protocol).

Subject incidence of all treatment-emergent, serious, treatment-related, serious treatment-related, those leading to withdrawal of investigational product, and fatal adverse events will be tabulated by system organ class and preferred term in descending order of frequency.

Where appropriate the tables will also be presented by worst grade.

The above adverse event tables will not be created if two or fewer subjects experience the adverse event.

Details of each adverse event will be listed. Listings and/or narratives of any on-study deaths, serious and significant treatment-emergent adverse events, including early withdrawals due to adverse events, also will be provided should they occur.

Dose Limiting Toxicities (DLT)

The probability of each TPI and of a DLT from the BLRM will be summarized by dose and group along with the estimated dose-toxicity curve. Subject incidence of DLT by dose level and group will be summarized.

As a sensitivity analysis, a one-parameter Continual Reassessment Method (CRM) model may be used to estimate the dose-toxicity relationship to help making dose escalation decisions.

Disease-Related Event (DREs)

Safety endpoints (eg, mortality and morbidity) that are study endpoints are reported on an eCRF. A negatively adjudicated safety endpoint will be reported to the investigator and treated by Amgen as appropriate. This could include no action, or a report on the eCRF as a Disease-Related event, an adverse event, or a serious adverse event.

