10.5.2 Primary Endpoint(s)

Dose Limiting Toxicities (DLT)

The DLT endpoint will be analyzed using the DLT Evaluable Analysis Set. The probability of each TPI and of a DLT from the BLRM will be summarized by dose and group along with the estimated dose-toxicity curve. Subject incidence of DLT by dose level and group will be summarized.

Adverse Events

Subject incidence of all treatment-emergent adverse events will be tabulated by system organ class and preferred term. The number and percentage of subjects reporting adverse events will be evaluated overall and by dose level and will also be tabulated by relationship to study drug.

Tables of fatal adverse events, serious adverse events, adverse events leading to withdrawal from investigational product or other protocol-required therapies, and significant treatment-emergent adverse events will also be provided.

Disease-Related Event (DREs)

Safety endpoints (eg, mortality and morbidity) that are study endpoints are reported on an eCRF. A negatively adjudicated safety endpoint will be reported to the investigator and treated by Amgen as appropriate. This could include no action, or a report on the eCRF as a Disease-Related event, an adverse event, or a serious adverse event.

Clinical Laboratory Tests

Clinical chemistry, hematology, and urinalysis data will be listed and reviewed for each subject. Values outside the normal laboratory reference ranges will be flagged as high or low on the listings. Depending on the size and scope of changes in laboratory data, summaries of laboratory data over time and/or changes from baseline over time may be provided. Tables of maximum shifts from baseline for selected laboratory values may also be provided.

Vital Signs

Vital signs data will be listed and reviewed for each subject. Depending on the size and scope of changes, summaries of vital signs data over time and/or changes from baseline over time may be provided.

Electrocardiograms

Summaries over time and/or changes from baseline over time will be provided for all ECG parameters.

Subjects' maximum change from baseline in QTc will be categorized and the number and percentage of subjects in each group will be summarized.

Subjects' maximum post baseline values will also be categorized and the number and percentage of subjects in each group will be summarized.

All on-study ECG data will be listed and select parameters of interest may be plotted.

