3.2 Sample Size

It is anticipated that around 82 subjects will be enrolled in the study. Up to 30 DLT-evaluable subjects will be enrolled in dose escalation Group 1 (recurrent disease) and up to 12 subjects in dose escalation Group 2 (maintenance setting). Up to 40 subjects will be enrolled in the dose expansion cohorts (15 subjects in Group 1 and up to 25 subjects in Group 2) at 9 or more sites across US, Australia and Europe.

The sample size in dose escalation is based on practical considerations and it is consistent with conventional oncology studies with the objective to identify the RP2D/MTD. With 2 subjects per cohort, there is a 19-56% probability of observing at least one DLT for a cohort if the true DLT rate is 10-33% and with 6 subjects per cohort, the probability is 47-91%.

The sample size of dose expansion Group 1 is based on practical considerations. With 21 subjects treated at the Group 1 RP2D/MTD (6 from dose escalation and 15 from dose expansion), there is a 66% probability of observing an adverse event with 5% incidence rate. For an ORR of 20%, the probability of observing the OR in at least 4 subjects

would be 63%. The estimated ORR and exact 80% CI for 4 responses is 19% and 9%-35% respectively.

The sample size for Group 2 dose expansion is based on a Bayesian predictive probability design (Lee, 2008). In Group 2, the ORR of interest is 20% or higher while an ORR of 5% or less is considered insufficient antitumor-activity. The maximum sample size is 31 subjects (6 from dose escalation and 25 from dose expansion). Futility will be assessed initially after treating 10 subjects for at least 6 months and continuously for each additional subject afterwards. If ORR is lower than 5%, enrollment may be terminated due to futility. The guidelines for early termination due to futility are as follows:

Number of Treated Subjects	Futility Termination Guideline
10	0 responders
19	1 or fewer responders
26	2 or fewer responders
31	3 or fewer responders

With this design, the probability of accepting the treatment is 0.05 (type I error) when ORR = 5% and 0.8 (power) when ORR = 20%. If the ORR is 5%, the probability of stopping the trial early at the interim with 10 evaluable subjects for futility is 60% and the expected additional subjects to be assessed in dose expansion is 9.6.

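### SAP 9.6.1 drops adverse event incidence tables when two or fewer subjects are affected, although protocol 10.5.2 promises them with no minimum count and SAP section 10 declares no change

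*SAP*

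**What the plan says.** SAP 9.6.1 sets out incidence tables by system organ class and preferred term for all treatment-emergent, serious, treatment-related and serious treatment-related events. It adds that "those leading to withdrawal of investigational product, and fatal adverse events will be tabulated by system organ class and preferred term". The restriction follows: "The above adverse event tables will not be created if two or fewer subjects experience the adverse event". No category is exempt, and the SAP does not say whether the count is made per preferred term or per table, or over which subjects.

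The same section keeps other outputs without a threshold:

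- Every event goes into a listing, whatever the count.
- For the graver outcomes the SAP adds: "Listings and/or narratives of any on-study deaths, serious and significant treatment-emergent adverse events, including early withdrawals due to adverse events, also will be provided".
- Under the DLT heading, "Subject incidence of DLT by dose level and group will be summarized".

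Protocol 10.5.2 commits to tabulating treatment-emergent events overall, by dose level and by relationship to study drug. It also promises "Tables of fatal adverse events, serious adverse events, adverse events leading to withdrawal from investigational product or other protocol-required therapies". It sets no minimum count. SAP section 10 states that nothing has changed from the protocol-specified analyses. SAP 9.6.2 tabulates number and percentage for any laboratory toxicity whose worst grade is 3 or 4 in one subject or more.

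**The concern.** Treatment-emergent and treatment-related adverse events are part of the primary endpoint (protocol 10.1.1, SAP 2.1). The protocol describes their analysis as counts and percentages, including by dose level. A listing gives each event in detail but not the incidence against a denominator, which a reader of a dose-escalation study needs in order to compare dose levels.

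Escalation cohorts hold one subject, then two to four. On a per-event reading, an event in both subjects of a two-subject cohort and in nobody else stays untabulated whether the count is per dose or study-wide.

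The rule also sits oddly beside SAP 9.6.2. A grade 3 laboratory value in one subject earns a table row, while a fatal adverse event in two subjects may not. The SAP gives no reason for the difference.

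**Working it through.** **Inputs.** Threshold: at least three affected subjects (SAP 9.6.1). Group 1 at the RP2D/MTD: 6 + 15 = 21 subjects (SAP 3.2, protocol 10.2). SAP total: about 82 (SAP 3.2). Current protocol: up to 100 in Arm 1 and up to 90 in Arm 2 (protocol 10.2). Formula: exact binomial, P(X ≥ r) with n subjects and true incidence p.

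**The plan's own figure.** SAP 3.2 says "there is a 66% probability of observing an adverse event with 5% incidence rate" among 21 subjects. P(X ≥ 1) = 1 − 0.95^21 = 1 − 0.3406 = 0.659, so 66% is reproduced.

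**Reading A: per event, within the 21 subjects, p = 5%.**

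- P(0) = 0.3406
- P(1) = 21 × 0.05 × 0.95^20 = 0.3764
- P(2) = 210 × 0.05² × 0.95^19 = 0.1981
- P(X ≥ 3) = 1 − 0.3406 − 0.3764 − 0.1981 = 0.085

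The event is seen but not tabulated with probability 0.3764 + 0.1981 = 0.575. That is 0.575 / 0.659 = 87% of the occasions on which it is seen. At 10% incidence P(X ≥ 3) is 35.2%, and at 15% it is 63.0%.

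**Reading B: per event, over all subjects, p = 5%.** For 82 subjects, P(0) = 0.0149, P(1) = 0.0643 and P(2) = 0.1371, so P(X ≥ 3) = 0.784.

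| Subjects counted | Incidence | Seen at least once | Reaches three, so tabulated |
|---|---|---|---|
| 21 (Group 1 at RP2D/MTD) | 5% | 65.9% | 8.5% |
| 82 (SAP total) | 5% | 98.5% | 78.4% |
| 90 (Arm 2, protocol) | 5% | 99.0% | 83.4% |
| 100 (Arm 1, protocol) | 5% | 99.4% | 88.2% |
| 82 (SAP total) | 2% | 80.9% | 22.6% |

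**Reading C: per table.** A table is dropped only if two or fewer subjects have any event in its category. If half of 21 subjects have some treatment-emergent event (an assumption; the documents give no rate), the chance of two or fewer is (1 + 21 + 210) / 2^21 = 232 / 2,097,152, about 0.01%. The all-treatment-emergent table is then safe, and a single-subject event still appears as a row in it. Sparse categories are exposed. If 2% of subjects had a fatal event (again an assumption), the 2% row above applies: with 82 subjects a fatal table would be warranted 80.9% of the time and produced 22.6% of the time.

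**The case against.** The best defence is that little information is lost. Individual listings and narratives for one or two subjects carry more detail than a near-empty table. DLT incidence by dose level and group is kept without a threshold. Dose decisions do not rest on these tables: the dose level review team sees all available data and every toxicity of grade 3 or higher (protocol 10.4.2), and the expansion hold on grade 4 or higher related events uses its own counts (protocol 10.2). All of this stands, and it limits the consequence.

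It also disposes of three stronger readings that a reader might reach:

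- **That the rule conceals deaths or serious events.** It does not; they remain in listings and/or narratives.
- **That the rule defeats the purpose for which the trial was sized.** SAP 3.2 and protocol 10.2 rest the Group 1 expansion size on practical considerations. The 66% is a quoted property of that size, not a design target.
- **That 8.5% is the general effect.** It holds only under Reading A. Nothing in SAP 9.6.1 says the count is made within those 21 subjects, or within a dose level.

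The objection does not answer the conflict between the documents. The protocol promises tables with percentages, the SAP withdraws some of them, and section 10 says nothing has changed. The SAP predates protocol Amendment 5, but that does not appear to explain it: for section 10.5.2, the amendment's change list records only an added sentence on the DLT analysis set.

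**Conclusion.** The point holds as an undeclared departure from protocol 10.5.2 that removes tabulated incidence for part of the primary endpoint. Its size cannot be fixed, because the threshold has no defined unit. For a 5% event the chance of tabulation is 8.5% if counted per event in 21 subjects and 78% if counted over 82, against 66% and 98.5% with no threshold. If the rule works per table, the loss falls mainly on sparse fatal, serious or withdrawal tables. These figures assume independent subjects with a common incidence. Two programmers could apply the sentence differently and both be compliant, which is a further reason to remove it. The change is worth making, but the underlying safety data and the DLT analysis are not at risk.

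**What to change.** Delete the sentence from SAP 9.6.1, so that every adverse event category with at least one affected subject is tabulated as protocol 10.5.2 describes. Where a category has no events, a one-line statement to that effect is enough; no empty table is needed.

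If the sponsor wishes to keep a threshold, the minimum is to exempt fatal, serious, treatment-related and withdrawal events. The SAP should then state whether the count is per preferred term or per table and over which subjects, and declare the departure in section 10.

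The cost is a few short tables. No new data, sample size or design change is involved.

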9.6.2 Laboratory Test Results

The number and percentage of subjects experiencing clinically significant worsening in serum chemistry, serum hematology, and coagulation labs will be presented overall for all subjects receiving investigational product. Clinically significant worsening is based on grade shifts using CTCAE version 4.0. Two tables will present these overall summaries.

1. For each laboratory toxicity with a worst grade of 3 or 4 in at least one subject, the number and percentage of subjects experiencing this laboratory toxicity at any grade, worst grade 3, and worst grade 4 will be presented. The direction of the laboratory worsening will be denoted (eg, decrease in platelets, increase or decrease in magnesium).
2. If required, laboratory parameters with a post-dose shift in at least one subject, the number and percentage of subjects experiencing a one grade shift, two grade shift, three grade shift, and four grade shift post-dose will be presented. The direction of the laboratory worsening will be denoted.

All laboratory data will be listed for the subject and laboratory of interest in order to provide proper context. Values outside the normal laboratory reference ranges will be flagged as high or low on the listings.

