10.5 Planned Methods of Analysis

10.5.1 General Considerations

The analyses described below will be reported separately for subjects enrolled to Arm 1 and for subjects enrolled to Arm 2. Unless otherwise specified, the analyses will be done using the Safety Analysis Set.

Descriptive statistics will be provided for selected demographics, safety, PK, PD, efficacy and biomarker data by dose, dose schedule, and time as appropriate. Descriptive statistics on continuous data will include means, medians, standard deviations and ranges, while categorical data will be summarized using frequency counts and percentages. ORR will be presented with 80% Clopper-Pearson exact CI using the RANO Evaluable Analysis Set. PFS will be summarized using Kaplan-Meier method. Graphical summaries of the data may also be presented.

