2.1 Objectives and Endpoints

Objectives	Endpoints
Primary	

 Evaluate the safety and tolerability of AMG 596 administered by continuous intravenous (cIV) infusion in subjects with EGFRvIII-positive glioblastoma in the recurrent setting (Group 1) and afterwards in the maintenance treatment phase of newly diagnosed glioblastoma (maintenance setting) (Group 2). 	
 Dose limiting toxicities (DLT), treatment-emergent adverse events, treatment-related adverse events and clinically significant changes in vital signs, physical examinations, and clinical laboratory tests.
Secondary	

 Evaluate the pharmacokinetics (PK) of AMG 596 in serum when administered by cIV infusion. 	
 PK parameters for AMG 596 including, but not limited to, average steady-state concentration (C_{ss}), area under the concentration-time curve (AUC), clearance, volume of distribution and half-life (t_{1/2}) for serum AMG 596.

 Evaluate the clinical benefit of AMG 596 as determined by objective response rate (ORR) per modified Response Assessment in Neuro-Oncology Criteria (RANO) in subjects with EGFRvIII-positive glioblastoma in the recurrent and in the maintenance setting. 	
 Objective response (OR) as per modified RANO, time to response, response duration and time to progression (TTP).

 Evaluate progression free survival (PFS) at 6 and 12 months after initiation of treatment. 	
 Progression free survival (PFS) at 6 and 12 months after treatment initiation.
Exploratory	

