- In first cohorts AMG 596 will be administered as a cIV infusion for [REDACTED] at escalating doses with N = 1 per cohort. In the single subject cohorts, only a limited number of subjects will be enrolled at dose levels anticipated to be lower than those at which visible pharmacodynamics activity including adverse events related to AMG 596 therapy will be expected. In addition, the investigator together with the subject will decide on subsequent treatment duration carefully. Subjects are allowed to stay on study in [REDACTED] cycles until discontinuation criteria apply.
- The DLT period is [REDACTED] DLT period 1 is from day [REDACTED] of AMG 596 infusion, and DLT period 2 is from day [REDACTED] of infusion (includes cycle 2).
- The cohort size will be increased to N = 2-4 subjects (ie, Start of Dose Escalation Phase 2, multiple subject cohorts) after observation of
 - Treatment-related adverse events of common terminology criteria for adverse events (CTCAE) grade 2 or higher and/or
 - Quantifiable cytokine levels in blood or CSF above baseline

Phase 2, Multiple subject cohorts:

- Subjects in the first multiple subject cohort receive the same dose as the last single subject cohort.
- All subjects receive [REDACTED] infusion cycles with [REDACTED] treatment break until treatment discontinuation criteria apply.
- In the first cycle, DLT period 1 is from day [REDACTED] of AMG 596 infusion and DLT period 2 is from day [REDACTED] of infusion.

It is anticipated that dose-escalation will proceed according to the pre-planned nominal doses though intermediate dose levels may be used if required after reviewing all available safety data.

When a first DLT is observed, the Bayesian logistic regression model (BLRM) will be used to guide dose level selection ([Neuenschwander et al., 2008](#)). The cohort size will be N = 2-4 subjects. After each cohort, the model's recommended MTD dose level for evaluation is the dose level with the highest probability of the target toxicity probability interval (TPI), but with a less than 0.25 probability of an excessive or unacceptable TPI. The target TPI is (0.20, 0.33], and TPIs of (0.33, 0.60] and (0.60, 1.00] are defined as excessive and unacceptable, respectively. The actual dose selected at each dose

decision may be at or below the model's recommended dose as determined by the DLRT after considering all information.

Stopping rules for Group 1: Recurrent Disease

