9.1 General Considerations

Descriptive statistics will be provided for selected demographics, safety, PK, PD, efficacy data by dose, dose schedule, and time as appropriate.

Descriptive statistics on continuous data will include means, medians, standard deviations and ranges, while categorical data will be summarized using frequency counts and percentages.

ORR will be presented with 80% Clopper-Pearson exact CI. PFS will be summarized using Kaplan-Meier method. Graphical summaries of the data may also be presented, eg. duration on study, changes in tumor load per time.

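### SAP 9.6.2 defines the laboratory worsening tables only as overall summaries; SAP 9.1 permits by-dose safety summaries but does not commit to them for laboratory data

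*SAP*

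**What the plan says.** SAP 9.6.2 (Laboratory Test Results) covers chemistry, hematology and coagulation. The number and percentage of subjects with clinically significant worsening, defined by CTCAE grade shift, "will be presented overall for all subjects receiving investigational product". It then says "Two tables will present these overall summaries": one for toxicities that reach grade 3 or 4 in at least one subject, and one, if required, for the size of the grade shift. Beyond that there are listings: "All laboratory data will be listed for the subject and laboratory of interest".

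Four other places bear on this.

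- SAP 2.1 puts "clinically significant changes in vital signs, physical examinations, and clinical laboratory tests" in the primary endpoint.
- SAP 9.1 gives the general rule: "Descriptive statistics will be provided for selected demographics, safety, PK, PD, efficacy data by dose, dose schedule, and time as appropriate". Protocol 10.5.1 has a matching line, "efficacy and biomarker data by dose, dose schedule, and time as appropriate", and requires the analyses to be reported separately for Arm 1 and Arm 2.
- SAP 3.1 says that the single-subject cohorts are "enrolled at dose levels anticipated to be lower than those at which visible pharmacodynamics activity" is expected.
- Protocol 10.5.2 says that the number and percentage of subjects reporting adverse events "will be evaluated overall and by dose level". Its laboratory paragraph promises listings and optional summaries over time, and does not mention dose.

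**The concern.** The escalation part exists to find the RP2D/MTD, so the natural way to read a laboratory toxicity is against dose. A programmer who follows SAP 9.6.2 as written would build one pooled column. Where the SAP wants a breakdown it says so: DLTs by dose level and group (9.6.1), objective response by dose received (9.5.1), PK by dose level (9.7.1). The laboratory section says overall twice.

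Pooling puts subjects treated well below the RP2D/MTD, and possibly some treated above it, into the same denominator as the subjects whose experience matters most for later development. The protocol itself expects some dose-related laboratory risk: sections 2.4.1 and 2.5.3.1 note that sucrose exposure at the highest planned doses raises a concern about renal function. A signal of that kind would be averaged over every dose in the only aggregate laboratory tables that the SAP defines.

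**Working it through.** **Stated figures.** The documents give no figure for the laboratory tables, so I checked the numbers that the calculation leans on.

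- SAP 3.2 total: 30 + 12 + 15 + 25 = 82, as stated.
- SAP 3.2, at least one event of 5% incidence in 21 subjects: 1 − 0.95^21 = 0.659, against 66% stated.
- SAP 3.2, at least 4 responses in 21 at a rate of 20%: 0.630, against 63% stated.

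**How many subjects are at other doses.** SAP 3.2 plans 21 Group 1 subjects at the RP2D/MTD (6 + 15) and up to 31 in Group 2 (6 + 25). That makes 52.

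| Population | Total | At RP2D/MTD | Other doses | Share at other doses |
|---|---|---|---|---|
| SAP 3.2 | 82 | 52 | (30 − 6) + (12 − 6) = 30 | 37% |
| Protocol 10.2, Arm 1 | 100 | 52 | (45 − 6) + (15 − 6) = 48 | 48% |
| Protocol 10.2, Arm 2 | 90 | 52 | (30 − 6) + (20 − 6) = 38 | 42% |

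**What the overall table would show.** With rate p at the RP2D/MTD and q at other doses, the pooled rate is (52p + n_other × q) / N. The rates are my assumptions; q runs from 0% to 5%.

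- SAP, p = 20%: (52 × 0.20 + 30 × 0) / 82 = 10.4 / 82 = 12.7%, up to (10.4 + 30 × 0.05) / 82 = 11.9 / 82 = 14.5%.
- SAP, p = 10%: 6.3% to 8.2%. SAP, p = 30%: 19.0% to 20.9%.
- Arm 1 under the current protocol, p = 20%: 10.4 / 100 = 10.4%, up to (10.4 + 2.4) / 100 = 12.8%.
- Arm 2 under the current protocol, p = 20%: 10.4 / 90 = 11.6%, up to (10.4 + 1.9) / 90 = 13.7%.

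**Which data have no other by-dose summary.**

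- DLTs are summarized by dose level and group. But protocol 6.2.3 excludes lymphopenia of any grade, and laboratory values of grade 3 or higher that are judged not clinically relevant and improve to grade 2 or lower within 72 hours (7 days for ALT and GGT). Events after the DLT window count only if the DLRT agrees unanimously.
- Adverse events are evaluated by dose level under protocol 10.5.2. But protocol 9.2.2.1 says that abnormal laboratory findings without clinical significance are, in general, not recorded as adverse events.
- What remains is laboratory grade shifts that are neither DLTs nor adverse events. For these the plan offers the overall tables and subject listings.

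**The case against.** The strongest reply is that SAP 9.1 already provides for safety data by dose, that the protocol promises no by-dose laboratory table, and that 9.6.2 therefore breaches nothing and is a matter of layout. Much of this stands. There is no conflict with the protocol: its by-dose sentence concerns adverse events, and the SAP's grade 3 or 4 table goes further than the protocol's laboratory paragraph. But 9.1 speaks of selected data where appropriate, while 9.6.2 is specific. The general line permits a by-dose table without committing anyone to produce it.

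Three stronger readings are tempting, and the documents do not support them.

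- A reader might infer that both arms share one denominator, so that a toxicity confined to the AMG 404 combination is diluted over all 190 subjects. Protocol 10.5.1 requires separate reporting by arm. The SAP (May 2019) predates the amendment that added Arm 2 (July 2019) and plans for 82 subjects.
- A reader might infer that the tables conceal any dose relation. They do not: listings exist, DLTs are shown by dose level and group, and laboratory changes that need treatment are adverse events, which the protocol evaluates by dose level.
- A reader might infer that the RP2D is chosen without laboratory data by dose. Protocol 10.4.2 has the DLRT review laboratory results and all toxicities of grade 3 or higher as the trial proceeds. The 9.6.2 tables are not the instrument for that decision.

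It is also fair that cells for early dose levels will hold one to four subjects, where percentages say little. That is a reason for a pooled RP2D/MTD column, not for a single overall one.

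**Conclusion.** The point holds as a gap in specification. Under SAP 9.6.2 as written, a component of the primary endpoint is tabulated only over all treated subjects, and no other section commits to laboratory summaries by dose. At planned maxima 37% of the SAP population is at other doses, and an assumed 20% rate at the RP2D/MTD would read as about 13% to 15%. The data affected are mainly grade shifts that are neither DLTs nor adverse events, so the consequence is modest and the change is an inexpensive improvement.

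The size rests on assumptions: the event rates are illustrative; enrolment reaches its planned maxima with exactly 6 escalation subjects per group at the RP2D/MTD; and the 52 combine two groups whose RP2D/MTD may differ. Some escalation counts are of DLT-evaluable subjects, so the number treated could be higher. Not every other dose is below activity. If toxicity at those doses were similar to that at the RP2D/MTD, the overall figure would mislead little.

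**What to change.** In SAP 9.6.2, present both tables by dose level received within group, and separately by arm as protocol 10.5.1 already requires. Add a pooled RP2D/MTD column (Part 1 subjects at the RP2D/MTD plus Part 2) and keep a total column.

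State how subjects with intra-subject dose escalation, which protocol 3.1 allows, are assigned, for example to the dose at onset of the worst grade. SAP section 6 says that subjects are analyzed by the dose they received, but that does not settle the matter for a subject who received more than one.

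The cost is longer tables, small cells at the early dose levels, and one added rule for assigning dose. No additional data collection is needed.
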